**Procedures performed for research purposes only:****Statistical Methods, Data Analysis and Interpretation**

---

The sensitivity/specificity and diagnostic accuracy of clinicians will be compared before and after the use of novel ROTEM app. The performance of more experienced clinicians will be

compared to those with little to no experience in ROTEM. Analysis will be done using a mixed effects model to account for clustering of measurements within clinician groups. Inter-rater reliability analysis will be done to assess the similarity within clinician groups using the ICC. The reference standard will be established using two cardiac anesthesiologists with specific expertise in ROTEM analysis. ICC will be used to characterize the inter-rater and intra-rater reliability of these experts to create the reference standard.

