## Background and Introduction

---

The evaluation and treatment of coagulopathy in the perioperative setting is critical to patient morbidity and mortality. Historically, the coagulation cascade was evaluated with laboratory studies such as prothrombin time (PT), partial thromboplastin time (aPTT) and platelet count. However, viscoelastic tests such as thromboelastography (TEG®) and rotational thromboelastometry (ROTEM®) have allowed for more specific investigation into clot formation, firmness, strength and lysis. Additionally, thromboelastography can help determine which type of blood product is deficient in this clot formation. This test is commonly used trauma and cardiac surgery, but also has applications in obstetrics, transplantation and critical care. Utilization of thromboelastometry has been shown in some studies to decrease costs and some blood product administration.

Although thromboelastometry can offer valuable information, the biggest challenge of this technology is the ability of clinicians to correctly interpret the data. Especially those practitioners that do not utilize this technology on a regular basis. This may lead to improper administration of blood products which could worsen outcomes.

A novel software was developed at our institution to help clinical providers to interpret rotational thromboelastometry (ROTEM®). There are multiple other thromboelastometry guiding applications currently available including TEG2GO, TEM/TEG Guide, and TICapp, however none have these have been validated with ROTEM.

**Hypothesis:** Our hypothesis is that a novel software program will improve the accuracy of ROTEM interpretation amongst practicing clinicians with a range of experience in ROTEM interpretation. Furthermore, we hypothesize that diagnostic accuracy will improve more for inexperienced clinicians than those with extensive ROTEM experience.

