**Sample Size:**

At Utah:

All Centers: 100

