**Inclusion Criteria:**

Current residents and attending physicians in the Department of Anesthesiology who have a range of experience and exposure to thromboelastography.

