**Recruitment/Participant Identification Process:**

Participants within the Department of Anesthesiology will be sent a email describing the study and with the informed consent document as an attachment to the email. Imbedded in the email will be an individual link to an online survey. Participants will be informed that by clicking the link they have consented to participation in the study. The online survey will include questions on duration of practice, clinical subspecialty if any, duration of experience with ROTEM, and perceived expertise in ROTEM. The participants when then be shown a series of ROTEM images and asked to interpret them. This will be followed by a short tutorial on the novel interpretation application. Finally, the participants will be shown a second series of ROTEM images and asked to interpret them now with the use of the novel interpretation application.

The study team will continually review participant enrollment and the degree of experience of the participants. If there appears to be developing a selection biased towards a certain level of experience the study team will actively seek out and recruit potential participants within the Department of Anesthesiology either by sending a further emails, in person, or through advertisement at faculty meeting or other community events.

If a participant elects not to participate in the study, they may inform the study team and no further attempts at recruitment will be made. Information as to who does and who does not participate in the study will not be communicated to the Department Chair, Vice Chairs, or Residency Directors.

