**Procedures:**

- Currently, ROTEM study results for each patient are printed and uploaded into the medical record.
- We will retrospectively review these ROTEM studies, de-identify them, and upload them to a database. This is covered under IRB 00096411
- An online survey will be developed using these de-identified images to test the ability of clinicians to correctly interpret ROTEM studies.
- Participants within the Department of Anesthesiology will be recruited by email with informed consent and a link to the survey.
- If the clinician participants consent to the study, they will open the link to the survey and will be asked a short series of questions on their clinical practice (years of training, type of clinical practice, and familiarity with ROTEM) and then shown 20 ROTEM images in random order.
- For each ROTEM image they will be asked to choose what intervention should be done (do nothing, give FFP, give platelets, etc...)
- After 20 images have been reviewed, an online version of the novel ROTEM App will be displayed in the survey and a brief tutorial will be given to demonstrate how to use it.
- The participant will then be shown 20 more study ROTEMs in random order and asked to interpret these studies in a manner similar to the beginning of the survey.
- Data will be recorded in RedCap
- A reference standard of correct responses will be created using the responses of two members of the study team who are known experts in ROTEM interpretation. This reference standard will be used to determine the sensitivity/specificity of clinician responses before and after the use of the App.

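### The second hypothesis rests on an undefined two-category experience contrast, although graded ROTEM experience is to be collected and a difference in improvement is what must be tested

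*Combined protocol and SAP*

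**What the plan says.** In the Combined protocol and SAP, Background and Introduction states the second hypothesis: "diagnostic accuracy will improve more for inexperienced clinicians than those with extensive ROTEM experience". This concerns a difference in improvement. Inclusion Criteria admits residents and attendings "who have a range of experience and exposure to thromboelastography".

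The survey items on experience are listed twice:

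- Recruitment/Participant Identification Process: "questions on duration of practice, clinical subspecialty if any, duration of experience with ROTEM, and perceived expertise in ROTEM".
- Procedures: "years of training, type of clinical practice, and familiarity with ROTEM".

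The recruitment section adds that "The study team will continually review participant enrollment and the degree of experience of the participants", so that recruitment can be steered if one level of experience dominates. It does not say how that level is measured.

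The Statistical Methods section then compares the performance of more experienced clinicians with that of others, "compared to those with little to no experience in ROTEM". It names a mixed effects model for clustering within clinician groups. It does not say which item defines experience, where any cut falls, how many groups there are, or where clinicians in the middle go. It mentions no experience term and no interaction between app use and experience.

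**The concern.** Three things are at stake for the second hypothesis.

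1. **Freedom of choice.** Several items could define experience and no cut is fixed. The grouping could be chosen after the responses are seen, and the answer could change with it.
2. **Lost information.** The plan sets out to enrol a spread of experience and to record its duration. A contrast of two categories ignores the grading within each category, or leaves out the middle.
3. **The wrong comparison.** A difference in performance between experience groups does not show whether the app helps one group more. Experienced clinicians may score higher both before and after the tutorial and still gain the same amount. Only the interaction addresses the hypothesis as stated.

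**Working it through.** **Inputs.** The documents supply one number, the sample size ("All Centers: 100"). They give no alpha, power, effect size, standard deviation or group sizes, so there is no planned figure to reproduce. Everything below rests on assumptions: a normally distributed experience score, a linear relation between that score and the gain in accuracy, one gain per clinician, and two-sided alpha 0.05.

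**Step 1: splitting everyone into two groups.** Relative to using the score linearly, a split at quantile q keeps a fraction φ(z_q)² / [q(1−q)] of the information.

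| Split | Calculation | Information kept | 100 clinicians worth about |
|---|---|---|---|
| 50/50 | 0.3989² / 0.25 | 0.637 | 64 |
| 70/30 | 0.3477² / 0.21 | 0.576 | 58 |
| 80/20 | 0.2800² / 0.16 | 0.490 | 49 |
| 90/10 | 0.1755² / 0.09 | 0.342 | 34 |

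**Step 2: comparing only the extremes.** The plan's wording could also mean a contrast of two tails, each holding a fraction p of clinicians. The difference in mean score is 2φ(z_p)/p and its variance is proportional to 2/(np), so the information kept is 2φ(z_p)² / p.

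- Outer thirds: 2 × 0.3636² / 0.3333 = 0.79.
- Outer 27%: 2 × 0.3307² / 0.27 = 0.81, about the best that equal tails can do.

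Both exceed the 0.64 of a median split. The loss is then about 19% to 21%.

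**Step 3: what this means for power at N = 100.** Let ρ be the assumed correlation between experience and gain. Power is Φ(atanh(ρ′)·√97 − 1.96), where ρ′ = ρ for the continuous score and ρ′ = ρ × √(information kept) for a split. For ρ = 0.28:

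- Continuous: atanh(0.28) = 0.288; 0.288 × 9.849 − 1.96 = 0.87; power 81%.
- Median split: ρ′ = 0.28 × 0.798 = 0.223; power 61%.
- 80/20 split: ρ′ = 0.28 × 0.700 = 0.196; power 50%.

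| ρ (assumed) | Continuous | 50/50 | 80/20 |
|---|---|---|---|
| 0.20 | 51% | 35% | 28% |
| 0.28 | 81% | 61% | 50% |
| 0.35 | 95% | 81% | 69% |

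A simulation of 10,000 data sets at ρ = 0.28 gave 81%, 62% and 50%.

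**Step 4: hypothesis against analysis.** Background and Introduction predicts a larger improvement in one group. The Statistical Methods section lists a before/after comparison and, separately, a comparison of performance by experience. Neither sentence combines the two, so the interaction is left unstated.

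**The case against.** **The magnitude is assumed.** This stands. No distribution, trend or split is given, so the percentages show direction and rough size only. An extreme-group contrast loses less than a median split, so leaving out the middle should not be counted as a further loss on top of it. Even so, some information is lost under each form examined here.

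**Duration may not be the best measure.** Background and Introduction places the difficulty with clinicians who do not use the technology regularly. That is frequency of use, and years of rare use would score high on duration. The benefit could also level off with experience. Both points are fair, so duration is offered only as an example and non-linearity should be checked.

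**Stronger readings that the documents do not support.**

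- A reader might infer that ROTEM experience is to be measured by years of training or by self-rated expertise. No section says so. Each list separates general practice or training from ROTEM-specific items, and the analysis refers to experience in ROTEM.
- A reader might infer that the two lists are rival scales. Both describe one survey, and the list under Procedures may simply paraphrase the other. That calls for aligned wording; it does not show a conflict of measurement.
- A reader might infer that clinicians will be misclassified. This is only a risk. It depends on an item and cut not yet chosen, and on how well that item tracks real exposure, which the documents do not say.
- A reader might infer that recruitment will be balanced on one scale and analysed on another. The recruitment section names no scale, so this cannot be shown.

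**The hypothesis is secondary.** This is also true. The stated purpose of the study is whether the software improves accuracy, and this point leaves the overall before/after comparison untouched.

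**Conclusion.** The concern holds in a limited form. The plan addresses its second hypothesis through a contrast of two experience categories with no defining item, no threshold and no place for the middle, and it does not state the interaction that the hypothesis needs. A continuous or ordered term would serve better and is available from an item the plan already lists.

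Under a normal score and a linear trend, the two-category contrast keeps about 64% of the information at a median split, 49% at 80/20 and at best about 81% for extreme groups. These figures would shift with a skewed score or a curved trend. The absence of a definition and of an interaction term is read directly from the text and needs no such assumption.

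**What to change.** Before any responses are seen:

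1. Name one ROTEM-specific primary measure of experience. One example, already in the recruitment section, is the first item in "duration of experience with ROTEM, and perceived expertise in ROTEM".
2. Align the item wording in the recruitment section and Procedures, and use the named measure in monitoring recruitment.
3. In the mixed model, enter the measure as a continuous or ordered term with an app-by-experience interaction, and make that interaction the test of the second hypothesis.
4. Check for non-linearity in the experience term.
5. Use perceived expertise as a sensitivity analysis, and show a two-group table, with its cut fixed in advance, as description.

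**Cost.** Wording in three sections. No extra participants are needed, and no new survey item if duration is the measure chosen; frequency of use would need one added question. The small downside is that the result is a slope or trend, so readers need the descriptive table beside it.

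### The second hypothesis is about a difference in gain, but the only experience comparison named is of performance, and no app-by-experience interaction is specified

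*Combined protocol and SAP*

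**What the plan says.** The Background and Introduction section states the second hypothesis as a comparison of improvements: "Furthermore, we hypothesize that diagnostic accuracy will improve more for inexperienced clinicians than those with extensive ROTEM experience".

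The Statistical Methods section names two comparisons. The first is before versus after, with no mention of experience: "The sensitivity/specificity and diagnostic accuracy of clinicians will be compared before and after the use of novel ROTEM app". The second sets the performance of more experienced clinicians against the others, "compared to those with little to no experience in ROTEM", with no mention of change. The model is then introduced by its handling of clustering: "Analysis will be done using a mixed effects model to account for clustering of measurements within clinician groups". Fixed effects, link function, contrasts and scale are not listed.

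The survey collects the experience data before any image is shown. The recruitment section lists "duration of experience with ROTEM, and perceived expertise in ROTEM", along with duration of practice and subspecialty. No section says which of these defines the experience groups, or where one group ends and the next begins.

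**The concern.** A hypothesis that one group improves more than another is a statement about the period-by-experience interaction. A difference in performance between groups is a statement about level. Experienced clinicians may score higher before the app, with it, or both, and none of these shows who gained more. An analyst who follows the Statistical Methods section literally would produce an overall before/after result and a between-group result. Neither addresses the second hypothesis, and the between-group result could be reported as though it did.

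Two further choices are open and could be made after the data are seen: which survey item defines experience and how it is grouped, and whether gain is measured in percentage points or in odds.

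**Working it through.** **No plan figure to reproduce.** The sample size is given as "All Centers: 100", with no alpha, power, effect size or variance, so it cannot be re-derived.

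**Inputs from the documents.** 100 clinicians. Before the app, each is "then shown 20 ROTEM images in random order"; a further 20 follow with the app.

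**Assumed inputs (not in the documents).** All accuracy rates; two experience groups split 50/50 (20/80 as an alternative); between-clinician SD of 0.5 on the logit scale; two-sided 5% tests; 80% power where a detectable difference is given.

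**Step 1: what each comparison estimates.** Let E0, E1 be the accuracy of experienced clinicians before and with the app, and I0, I1 the same for inexperienced clinicians.

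- Second hypothesis: D = (I1 − I0) − (E1 − E0), which equals (E0 − I0) − (E1 − I1), the gap before minus the gap after.
- Post-app level comparison: E1 − I1, which is only one of those two gaps.
- Level comparison averaged over both periods: half the sum of the two gaps, not their difference.

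**Step 2: two illustrative cases.** These used 4,000 simulated trials each, 50 clinicians per group, 20 + 20 binary images per clinician, and Welch t-tests on clinician-level proportions.

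| Case (assumed rates) | D | Averaged gap | Post-app gap | Averaged level test rejects | Post-app level test rejects | Difference-in-gain test rejects |
|---|---|---|---|---|---|---|
| A: experienced 65%→80%, inexperienced 45%→60% | 15 − 15 = 0 | (20 + 20)/2 = 20 | 80 − 60 = 20 | 100% | 100% | 5.2% |
| B: experienced 80%→80%, inexperienced 60%→80% | 20 − 0 = 20 | (20 + 0)/2 = 10 | 80 − 80 = 0 | 99% | 4.8% | 100% |

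The rates are those of a typical clinician. After averaging over clinicians, D is −0.4 points in case A and 19.4 points in case B. In A the hypothesis is in effect false, yet both level tests reject. In B it is true, yet the post-app level test rejects only at its nominal error rate. The averaged level test rejects almost always in both cases, so it cannot tell them apart.

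**Step 3: precision of the right test.** SD of one clinician's change = √(2p(1 − p)/20 + s²), where s is the SD of true change between clinicians. With p = 0.7 and s = 0 this is √(0.42/20) = 0.145.

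- Overall change: SE = 0.145/√100 = 0.0145.
- Difference in gain, 50/50: SE = 0.145 × √(1/50 + 1/50) = 0.0290, a ratio of 2.0.
- Difference in gain, 20/80: SE = 0.145 × √(1/20 + 1/80) = 0.0362, a ratio of 2.5.

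The ratios do not depend on p or s. Over p from 0.6 to 0.8 and s of 0 or 0.10, the detectable difference in gain is about 7 to 10 points (50/50) or 9 to 13 points (20/80), against 3.5 to 5 points for the overall change. Power for a 5-point difference in gain is 27–51% (50/50) or 19–35% (20/80).

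**Step 4: scale.** Take experienced 80%→90% and inexperienced 50%→65% (assumed). In points, the gains are 10 and 15, so the inexperienced gain more. In log-odds, they are ln(9/4) = 0.81 and ln(1.857/1) = 0.62, so the experienced gain more. The direction reverses on the same data.

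**The case against.** The strongest reply is that the plan does not exclude the right test. The fixed effects of the mixed model are unlisted, so they could include the interaction. The word performance comes directly after the before/after sentence and can be read to cover change. Every clinician is measured in both periods and asked about experience. All of this stands: the design can test the second hypothesis. A reader might infer that the plan commits to a levels-only comparison, or that the hypothesis cannot be tested; the text supports neither. What remains is that no section says which test answers the hypothesis, and the comparison that is named points elsewhere.

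Other inferences are tempting but unsupported. The plan does not propose separate before/after tests within each experience group, so an error rate for that practice would not describe this plan. It gives no accuracy rates, so a ceiling effect in experienced clinicians is plausible but undocumented. It does not state a median split or say that clinicians of middling experience are dropped. A contrast of groups also matches the hypothesis, which itself sets inexperienced against extensively experienced clinicians.

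On weight, the hypothesis is introduced as an addition to the first, and the Purpose and Objectives section covers only whether the software improves accuracy.

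**Conclusion.** The point holds as a mismatch between the second hypothesis and the analysis named for it. The hypothesis concerns a difference in gain, while the named experience comparison concerns performance. A comparison of levels can be significant when gains are equal and, in its post-app form, null when only inexperienced clinicians gain. The mismatch itself is read directly from the text. The rejection rates in the two cases rest on assumed accuracy rates, an assumed 50/50 split and an assumed between-clinician SD, so they show what can happen rather than what is expected.

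This should be fixed before analysis. A reader might take it as a defect that invalidates the trial; it is not, because the overall before/after comparison is untouched and the data for the right test are already to be collected.

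**What to change.** Add to the Statistical Methods section that:

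- the second hypothesis is tested by the period (before app, with app) × ROTEM-experience interaction in the planned mixed model, with all participants included;
- experience is taken from the survey items answered before the images, and the variable and any grouping are fixed before analysis;
- the difference in gain is reported in percentage points as the primary scale, standardised from the model, with the ratio of odds ratios beside it so that any dependence on scale is visible.

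Whether duration of ROTEM experience or perceived expertise is the main variable is a matter of preference. What matters is that one is named in advance; the other can serve as a sensitivity analysis.

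The cost is a few sentences, with no new data and no design change. The drawback is precision: with a standard error about 2 times that of the overall change under a 50/50 split (2.5 times under 20/80), the answer to the second hypothesis will be less certain. It should be reported with its confidence interval, and a non-significant interaction should not be read as evidence of equal gains.

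### The ICC is named for reader agreement without stating what is rated; if it is computed on the coded choice of intervention, its value depends on arbitrary codes

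*Combined protocol and SAP*

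**What the plan says.** Under Procedures, the plan describes the response to each image: "For each ROTEM image they will be asked to choose what intervention should be done (do nothing, give FFP, give platelets, etc". Participants see 20 images before the app tutorial and 20 more with the app. The key comes from experts: "A reference standard of correct responses will be created using the responses of two members of the study team".

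The section Statistical Methods, Data Analysis and Interpretation names the ICC twice. For participants: "Inter-rater reliability analysis will be done to assess the similarity within clinician groups using the ICC". For the experts: "ICC will be used to characterize the inter-rater and intra-rater reliability of these experts to create the reference standard".

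The plan does not state the variable on which either ICC is computed, any numeric coding, the form of ICC, or whether a participant may select more than one intervention. No agreement statistic for categorical data appears.

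**The concern.** An ICC is a ratio of variances, so it needs numbers, and the distances between those numbers count. Doing nothing, giving plasma and giving platelets have no order and no distances. Coded 1, 2, 3, a disagreement between the first and third option weighs four times as much (squared distance 4 against 1) as one between the first and second. Reordering the list reverses this while the readers' answers stay the same.

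The experts' agreement is the only evidence the plan offers that its reference standard is reliable, and every sensitivity, specificity and accuracy figure is scored against that standard. A reliability figure that moves with list order is weak support for it. With no coding fixed in advance, the order could also be settled after the data are seen.

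**Working it through.** The plan gives no ICC value, target or precision, so there is no figure to reproduce. The check asks how far the ICC moves when only the labels change.

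**Inputs.** From the plan: 20 + 20 = 40 images, two experts, three named options in an open-ended list. Assumed, because the plan is silent: both experts read all 40 images, one choice per image, five options, reader 1 uses each option 8 times, and the readers agree on 32 of 40 images (80%).

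**Formulas.**
- Cohen's kappa = (Po − Pe)/(1 − Pe).
- ICC(2,1), for n images and k readers, = (MSR − MSE) / (MSR + (k − 1)MSE + k(MSC − MSE)/n). MSR, MSC and MSE are the mean squares for images, readers and residual.

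**One fixed set of answers.** Call the options A to E. Reader 2 differs on 8 images: four A read as B, four C read as D.
- Kappa: reader 1 uses each option with proportion 0.2, so Pe = 0.2 whatever reader 2 does. Kappa = (0.80 − 0.20)/(1 − 0.20) = 0.75 under all 5! = 120 codings.
- ICC with A–E coded 1, 2, 3, 4, 5: MSR 3.774, MSC 0.800, MSE 0.082. (3.774 − 0.082)/(3.774 + 0.082 + 2 × 0.718/40) = 3.692/3.892 = 0.95.
- ICC with A–E coded 1, 4, 5, 2, 3: MSR 2.564, MSC 0, MSE 0.923. (2.564 − 0.923)/(2.564 + 0.923 − 2 × 0.923/40) = 1.641/3.441 = 0.48.
- Over all 120 codings the ICC runs from 0.48 to 0.96.

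**Dependence on where the disagreements fall.** Agreement is held at 80% with five options:

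| Disagreement pattern | ICC over the 120 codings |
|---|---|
| All 8 on one option pair | 0.20 to 0.95 |
| 8 on 8 different pairs | from 0.69–0.82 (narrowest) to 0.70–0.85 (widest) |
| 50 images, one on each of the 10 pairs, directions balanced | 0.754 throughout |
| 300 random patterns, 40 images | gap (highest minus lowest) 0.13 to 0.60, median 0.32 |

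The even pattern shows no movement because the sum of squared code distances over all pairs is the same for every ordering.

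**Three options only.** Reader 1 uses them 14, 13 and 13 times, and reader 2 reads 8 of the first as the second. Kappa is 0.70. The ICC is 0.42, 0.83 or 0.87 depending on coding.

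**A group.** Ten raters, 20 images, five options, about 30% errors concentrated on particular pairs: Fleiss' kappa is 0.47 and the ICC runs from 0.14 to 0.90.

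**Two categories.** On a yes/no indicator for option A in the first data set, the ICC is 0.62 under every coding tried, and kappa for that indicator is also 0.62. The coding problem therefore needs three or more categories.

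**The case against.** The strongest reply is that the plan never says the ICC will be run on coded choices. Sensitivity, specificity and accuracy all require 0/1 data, and the sentence before the clinician-group ICC specifies a mixed model for clustering. A reader could take that ICC as one on correct/incorrect scores or on per-intervention indicators, and on such data labels do not matter. This stands: for clinician groups the concern is conditional. The reading still has a cost. Correctness scores measure similarity in being right, and two readers who are wrong in different ways count as agreeing. In the ten-rater example the ICC on correctness is −0.04, against a Fleiss' kappa of 0.47 on the choices.

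The reply does not reach the experts. Their answers create the key, so they cannot be scored against it. Their ICC must rest on the choices themselves or on indicators that the plan does not define.

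Three stronger readings are tempting, and the documents support none of them:
- A reader might infer that the plan commits to an ICC on arbitrary codes. It names no rated variable and does not say whether the question is single-choice.
- A reader might infer that the ICC will necessarily swing from poor to excellent. The swing depends on a disagreement pattern that the documents do not give, and it can be nil.
- A reader might infer that the trial's main result is compromised. No threshold or decision rule uses the ICC, and the before/after comparison is a separate analysis.

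**Conclusion.** The concern holds in conditional form. As written, the plan pairs an interval-scale statistic with a response of three or more unordered categories and states no rated variable. If the coded choice is what is rated, the reported ICC is partly a product of list order. Under the assumed 80% agreement on five equally used options, the gap across codings is typically about 0.3, with 0.13 to 0.60 over random patterns. Contrived patterns extend this from zero (disagreements even over all pairs) to 0.75 (all on one pair: 0.95 − 0.20). These sizes illustrate the mechanism and do not predict this study's values.

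The point weighs most for the expert sentence and less for the clinician-group sentence, where a 0/1 reading remains open. It bears on how the reliability of the reference standard is described. It should be corrected, but it is not a threat to the accuracy analysis.

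**What to change.** Reword the two ICC sentences:

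- **Rated variable.** State that it is the intervention chosen for each image, and whether one or several may be selected.
- **Experts.** Replace the ICC with unweighted Cohen's kappa and raw percent agreement, with a confidence interval. Report intra-rater kappa only for images that the experts read twice. The plan describes no second expert read, so it should say whether one is planned.
- **Clinician groups.** Use a nominal multi-rater kappa such as Fleiss', separately for unaided and aided reads, with confidence intervals.
- **If several interventions can be selected.** Compute agreement for each intervention as yes/no.

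The cost is a rewording of two sentences and a little extra analysis. Inter-rater agreement needs no new data. Intra-rater agreement needs repeat reads by the experts if none are already planned.
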